## 2.3 Crude incidence and related risk estimates

### 2.3.1 Crude incidence and 100\*(1- $\alpha$ )% confidence interval

For  $n$  subjects, each at risk to experience a certain event with probability  $\pi$ , the crude incidence is estimated as  $p=x/n$ , where  $x$  is the number of subjects with the event.

Absolute and relative frequencies will be displayed as well as 95% confidence interval for the relative frequency based on the score method including continuity correction ([Newcombe 1998](#)).

With  $z$  as  $(1-\alpha/2)$ -quantile of the standard normal distribution (SAS:  $z=PROBIT(1-\alpha/2)$ ),  $n$  as total number of subjects (i.e. number of subjects in the denominator), and  $p$  as estimated crude incidence (number of subjects with event /  $n$ ) it is  $q = 1 - p$ .

Then the lower limit is

$$L = \max\left(0, \frac{2np + z^2 - 1 - z\sqrt{z^2 - 2 - \frac{1}{n} + 4p(nq+1)}}{2(n+z^2)}\right)$$

and the upper limit is

$$U = \min\left(1, \frac{2np + z^2 + 1 + z\sqrt{z^2 + 2 - \frac{1}{n} + 4p(nq-1)}}{2(n+z^2)}\right).$$

Note: if  $p = 0$  then  $L = 0$  and if  $p = 1$  then  $U = 1$ .

If appropriate, an exact 100\*(1- $\alpha$ )% confidence interval ([Clopper-Pearson 1934](#)) will be obtained by using the SAS procedure PROC FREQ with the EXACT BINOMIAL statement.

However, the confidence interval derived via the score method including continuity correction will be the default in safety analyses.

## 2.4 Exposure adjusted incidence rate and related risk estimates

### 2.4.1 Exposure adjusted incidence rate and $100*(1-\alpha)\%$ confidence interval

It will be assumed that for each of  $n$  subjects in a clinical trial the time  $t_j$  ( $j=1, \dots, n$ ) to the first occurrence of a certain treatment emergent event is observed, or if the event was not experienced, the (censored) time to the end of the observation period or last dose plus 84 days whichever occur earlier. The sequence of first occurrences of an event will be modeled to follow approximately a Poisson process with constant intensity  $\theta$ . The rate parameter  $\theta$  will be estimated as  $\lambda=D/T$ , where  $T = \sum_{j=1}^n t_j$  and  $D$  is the number of subjects with at least one event.

Conditionally on  $T$ , an exact  $100*(1-\alpha)\%$  confidence interval for a Poisson variable with parameter  $\theta T$  and observed value  $D$  can be obtained based on (Garwood, 1936), from which an exact  $100*(1-\alpha)\%$  confidence interval for  $D/T$  will be derived as follows (Sahai, 1993; Ulm, 1990):

$$\text{Lower confidence limit } L = \frac{0.5c_{\alpha/2,2D}}{T} \text{ for } D>0, 0 \text{ otherwise,}$$

$$\text{Upper confidence limit } U = \frac{0.5c_{1-\alpha/2,2D+2}}{T}$$

where  $c_{\alpha,k}$  is the  $\alpha$ th quantile of the Chi-square distribution with  $k$  degrees of freedom.

## 2.5 Subject reported outcomes

### 2.5.1 Dermatology Life Quality Index (DLQI)

The DLQI is a 10-item general dermatology disability index designed to assess Health-related quality of life in adult subjects with skin diseases (e.g. psoriasis). The measure is self-administered and includes six domains of symptoms and feelings, daily activities, leisure, work and school, personal relationships and treatment.

The scoring of each question is as follows:

- Very much: Scored 3
- A lot: Scored 2
- A little: Scored 1
- Not at all: Scored 0
- Not relevant: Scored 0
- Question unanswered: Scored 0
- Question 7: "prevented work or studying": Scored 3

The DLQI total score will be calculated by summing the score of each question resulting in a maximum of 30 and a minimum of 0. The higher the score, the more Quality of Life is impaired.

Meaning of DLQI Scores:

- 0-1= no effect at all on subject's life
- 2-5= small effect on subject's life
- 6-10= moderate effect on subject's life
- 11-20= very large effect on subject's life
- 21-30= extremely large effect on subject's life

The DLQI will be analyzed under six headings as follows:

- Symptoms and feelings: questions 1 and 2, score maximum 6
- Daily activities: questions 3 and 4, score maximum 6
- Leisure: questions 5 and 6, score maximum 6
- Work and school : question 7, score maximum 3
- Personal relationships: questions 8 and 9: score maximum 6
- Treatment: question 10, score maximum 3

Interpretation of incorrectly completed questionnaires:

There is a very high success rate of accurate completion of the DLQI. However, sometimes subjects do make mistakes.

1. If one question is left unanswered this is scored 0.
2. If two or more questions are left unanswered the questionnaire will not be scored.
3. If question 7 is answered 'yes' this will be scored 3. If question 7 will be answered 'no' or 'not relevant' but then either 'a lot' or 'a little' is ticked this will then be scored 2 or 1, respectively.
4. If two or more response options are ticked, the response option with the highest score will be recorded.
5. If there is a response between two tick boxes, the lower of the two score options will be recorded.
6. If one item is missing from a two- item subscale that subscale will not be scored.

Handling of missing values:

- If there is only one missing score per visit, it will be imputed with 0, and then the subscale including this item and the total score are derived accordingly.
- If there are two or more missing scores per visit, LOCF will be applied to the individual question scores, subscale scores, and total score, separately (i.e. LOCF is NOT applied to the 10 individual question scores for further derivation of the 6 subscale scores and 1 total score).

Of note, in situations where subjects responded to more questions than what was expected or required, the “most severe” answer was entered into the WriteResult (vendor for PRO data) database. In most cases the Self-Evident Corrections (SECs) were defined correctly, however, the SEC regarding question 7A/7B was not designed to select the “most severe” answer. This was confirmed with Novartis HEOR and communicated to the AIN team.

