9.4.3 Handling of missing values/censoring/discontinuations

Missing values in efficacy analyses, except for maintenance of response will not be imputed. All analyses will be based on observed values only.

For maintenance of response, please see definition below, missing values with respect to response variables based on PASI score score will be imputed with non-response regardless to the reason for missing data (e.g. premature study discontinuation, missed visit, administrative issues). Following the intent-to-treat principle for subjects who prematurely discontinue treatment, but who are observed in the follow-up period, efficacy data collected in follow-up periods will be linked to planned but missed study visits as well, following imputation schemes described in the analysis plan.

Subjects who opt to change treatment regimen or dose level and move into open-label treatment with 300 mg s.c. secukinumab every four weeks for the remainder of the trial will be considered as non-responders in the analysis of maintenance of response.

For other efficacy analyses they will not be considered after the timepoint of switching.

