### **1.8.4 Handling of missing values/censoring/discontinuations**

As observed value (Follow-up assessment excluded) will be reported primarily for both efficacy and PROs.

Response variables based on PASI score and IGA mod 2011 categories will be imputed with multiple imputation (MI) (Follow-up assessment excluded) as secondary analysis method. Summary tables for PASI scores and IGA mod 2011 categories will also be imputed using MI. Other response variables (e.g. DLQI 0 or 1 achievement) will be imputed with LOCF (Follow-up assessment excluded).

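### SAP 2.5.1 gives two incompatible results for a two-item DLQI subscale with one missing item, and neither it nor 1.8.4 sets limits on LOCF for DLQI

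*SAP*

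**What the plan says.** **Numbered scoring rules, SAP 2.5.1.** Rule 1 scores a single unanswered question as 0. Rule 2: "If two or more questions are left unanswered the questionnaire will not be scored". Rule 6: "If one item is missing from a two- item subscale that subscale will not be scored". The response list earlier in the section also has the line "Question unanswered: Scored 0", with no limit on the number of items.

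**Missing-value bullets, SAP 2.5.1.** For one gap: "If there is only one missing score per visit, it will be imputed with 0, and then the subscale including this item" and the total are derived. For more: "If there are two or more missing scores per visit, LOCF will be applied to the individual question scores, subscale scores, and total score, separately". A parenthesis adds that the carried item scores are not used to rebuild the subscales or the total.

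**SAP 1.8.4.** As-observed values, without follow-up assessments, "will be reported primarily for both efficacy and PROs". PASI and IGA responses receive multiple imputation as a secondary method. Then: "Other response variables (e.g. DLQI 0 or 1 achievement) will be imputed with LOCF", again without follow-up assessments. No stopping point is given.

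**Protocol 9.4.3.** "Missing values in efficacy analyses, except for maintenance of response will not be imputed". The next sentence limits all analyses to observed values.

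**SAP 1.1.1.** The declared changes include dropping non-responder imputation and providing multiple imputation for PASI and IGA responses. LOCF for DLQI is not among them.

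**The concern.** DLQI change and DLQI 0/1 achievement are two of the secondary objectives (Protocol 2.2), and both documents derive seven DLQI scores: six subscales and the total. Two programmers following different lines of SAP 2.5.1 would produce different subscale tables from the same forms.

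The LOCF bullet raises a second problem. It stands in the scoring section, is unconditional and is not assigned to a particular analysis. The SAP therefore does not settle whether an as-observed DLQI table may contain a carried-forward score.

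Third, LOCF for DLQI 0/1 departs from the protocol's observed-values rule without being declared. With no stop rule, it can carry a value past treatment discontinuation or past the Week 156 switch.

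**Working it through.** **1. The plan's own figure.** Ten items scored 0 to 3 give 10 × 3 = 30. The subscale maxima give 6 + 6 + 6 + 3 + 6 + 3 = 30. Both match the stated maximum of 30.

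**2. One item missing.** Four subscales have two items (questions 1–2, 3–4, 5–6, 8–9). Questions 7 and 10 are single-item subscales.

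| | Numbered rules | First bullet |
|---|---|---|
| Total score | item = 0, scored (rule 1) | item = 0, scored |
| Two-item subscale containing the gap | not scored (rule 6) | item = 0, scored |

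- Single-gap patterns in conflict: 4 × 2 = 8 of 10. Only questions 7 and 10 escape.
- Under zero-fill the subscale can reach only 0 + 3 = 3 of 6.
- The total agrees under both, so this conflict changes the subscale results but not DLQI 0/1.

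**3. Two or more items missing.**

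- Two-item gap patterns: 10 × 9 / 2 = 45.
- If both gaps lie in one subscale, 6 − 1 = 5 subscales remain complete. Otherwise 6 − 2 = 4 remain complete.
- Rule 2 discards these complete subscales. The LOCF bullet does not say whether they keep their current values.
- Items, subscales and total are carried separately, so carried subscales need not sum to the carried total.
- The unlimited zero-score line in the response list allows a third reading.

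**4. How far LOCF could carry.** The treatment period ends at Week 260 (Protocol 3.1). If LOCF runs to that visit, a last value at Week 104 is carried 260 − 104 = 156 weeks (about 3 years), and one at Week 156 is carried 260 − 156 = 104 weeks (about 2 years). This follows from the absence of a limit; the SAP does not state it.

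**5. Direction of LOCF for DLQI 0/1.** Let *r* be the rate among subjects observed, *m* the proportion missing, and *l* the proportion of leavers at DLQI 0/1 at their last value.

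- LOCF rate = r(1 − m) + ml
- LOCF minus as-observed = m(l − r)

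The documents give none of these for DLQI. As a guide to *m*, 108 of 675 subjects (16%) had discontinued by Amendment 1 (Protocol, Amendment 1 rationale). I take *m* from 16% to 30%, with *l* from 40% to 60% and *r* = 70% as assumptions.

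- r = 0.70, m = 0.30, l = 0.50: 0.49 + 0.15 = 0.64, against 0.70 as observed, a difference of −6 points.
- Over the assumed ranges: from 0.16 × (0.60 − 0.70) = −1.6 points to 0.30 × (0.40 − 0.70) = −9 points.
- The difference is zero when l = r and positive when l > r. The sign therefore depends on who leaves.

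**The case against.** The strongest defence has five parts.

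- **As-observed is the primary report for patient-reported outcomes.** LOCF for DLQI 0/1 is additional. This stands. A reader might infer that LOCF determines the reported DLQI result; SAP 1.8.4 does not support that.
- **Rule 2 and the LOCF bullet can be successive steps.** The form is unscored, the visit is therefore missing, and LOCF then fills it. This is a fair reading, so a flat contradiction between the two cannot be claimed. The link is still unstated, and nothing confines the second step to a sensitivity analysis. Equally, no text says that carried values do enter the as-observed tables.
- **DLQI is quality of life, not efficacy.** The protocol places it in 9.5.4, and the first sentence of 9.4.3 concerns efficacy. This softens the conflict but does not remove it: the following sentence of 9.4.3 covers all analyses, and the SAP itself lists DLQI with the efficacy data in Tables 1-9 and 1-14.
- **The carried value is normally an end-of-treatment value.** Subjects who stop early should have the Week 260 assessments, which include the DLQI, about four weeks after their last dose (Protocol 3.1 and 5.5.9, Table 6-1). LOCF also carries failures as well as successes. Both points stand.
- **Item gaps should be few.** Coordinators check the forms for completeness (Protocol 6.6.3), and SAP 2.5.1 says that completion is usually accurate. This limits how often the subscale conflict arises, but one defined result is still needed.

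A reader might also conclude that LOCF inflates DLQI 0/1 by 6 to 18 points. That range is m × l, from 0.16 × 0.40 = 0.064 to 0.30 × 0.60 = 0.18. It compares LOCF with counting missing as not achieved, which the SAP does not plan for DLQI. It does not measure inflation of the primary result.

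**Conclusion.** The point holds in three parts.

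1. **Subscale scoring is contradictory.** Rule 6 and the zero-fill bullet cannot both be applied in 8 of the 10 single-item gaps. This rests on the SAP text alone.
2. **The LOCF bullet in 2.5.1 is unlinked.** It is tied neither to rule 2 nor to a named analysis, so the content of the as-observed DLQI summaries is left open.
3. **LOCF for DLQI 0/1 is an undeclared departure from Protocol 9.4.3 and has no stop rule.** It is not the primary analysis. Its direction against as-observed is not fixed; the fall from 70% to 64% rests on the assumed 30% missing and 50% of leavers at DLQI 0/1.

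Carry-forward over years is possible under the text but is not stated in it. How many forms are affected cannot be derived from the documents. The consequence is confined to secondary, descriptive DLQI results: the primary objective is safety, and SAP 1.8.3 plans no hypothesis tests.

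**What to change.** **SAP 2.5.1.** Keep rules 1, 2 and 6. State that rule 1 applies to the total score and to any subscale not covered by rule 6. Delete the two missing-value bullets, so that as-observed DLQI summaries contain no carried-forward values and no zero-filled two-item subscale. Make the line that scores an unanswered question as 0 subject to these rules, and confirm that rule 2 also leaves the remaining complete subscales unscored.

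**SAP 1.8.4 and 1.1.1.** Either drop LOCF for DLQI 0/1, or keep it only as a labelled sensitivity analysis that stops at treatment discontinuation or switch, and list it in 1.1.1.

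**Cost.** A few lines of text and small programming edits. A few more subscale scores will be missing and denominators will be slightly smaller; under rule 2, a form with two gaps loses four or five complete subscales. With one gap in a two-item subscale, the total is scored and that subscale is not, so the reported subscales will not sum to the total. A table note should say so.

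Replacing LOCF with multiple imputation is a separate choice. The model in SAP 2.2.2 covers only PASI change and IGA, so DLQI would need its own specification.

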6.6.3 Health-related Quality of Life

The impact of psoriasis on various aspects of subject's health-related quality of life will be assessed by the following validated instruments:

- Dermatology Life Quality Index (DLQI[®])
- EuroQOL 5-Dimension Health Status Questionnaire (EQ-5D[®])
- Health Assessment Questionnaire- Disability Index (HAQ[®]-DI) (subjects with PsA from study CAIN457A2304 only)

At the appropriate scheduled visits (see [Table 6-1](#)), questionnaires are to be completed by each subject in the language with which she/he is most facile, and **before** she/he sees the Investigator for clinical assessments. Responses will be collected using digitized paper with a digital pen. The digitized paper will serve as source documentation; the pen will be transferred to its docking station for transmittal of the subject's responses to the vendor's database. Subjects are to complete the "Patient Reported Outcome (PRO) - Completion confirmation by the patient" page after completing all the questionnaires of a visit. This document will not be sent to the sponsor but kept at site in source documents.

The subject is to be given sufficient space and time to complete the questionnaires. The study coordinator is to check the questionnaires for completeness and encourage the subject to complete any missing responses. The original questionnaires will be kept with the subject's file as source documentation.

Completed questionnaires will be reviewed and examined by a blinded staff member at the site (not the Investigator or evaluator of the subject for the physician assessments), before the clinical examination, for responses that may indicate potential AEs or SAEs. The Investigator is to review not only the responses to the questions in the questionnaires but also to look for unsolicited comments written by the subject. If AEs or SAEs are confirmed by the Investigator, then she/he must record the events as per instructions given in [Section 7](#) of the protocol.

Investigators and study coordinators are not to encourage subjects to change the responses reported in the completed questionnaires. Study coordinators are to complete the header information at the top of the questionnaire prior to distributing it to the subjects.

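### SAP 2.5.1 discloses that the vendor's rule for DLQI question 7A/7B breaks the SAP's own scoring rules, but plans no correction, count or sensitivity analysis

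*SAP*

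**What the plan says.** SAP 2.5.1 sets the DLQI scoring. Among its rules for incorrectly completed questionnaires, rule 3 opens: "If question 7 is answered 'yes' this will be scored 3". It goes on to give 2 or 1 when 'no' or 'not relevant' is combined with 'a lot' or 'a little'. Rule 4 reads: "If two or more response options are ticked, the response option with the highest score will be recorded".

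The question 7 score goes directly into three outcomes:
- the subscale ("Work and school : question 7, score maximum 3");
- the total ("The DLQI total score will be calculated by summing the score of each question");
- DLQI 0/1 achievement, which is derived from the total.

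The closing note of the same section explains that, "in situations where subjects responded to more questions than what was expected or required", the vendor's database received the most severe answer. It says most of the vendor's corrections were set up properly and then names one exception: "however, the SEC regarding question 7A/7B was not designed to select the" most severe answer. The note ends: "This was confirmed with Novartis HEOR and communicated to the AIN team".

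Nothing further follows. SAP 1.1.1, on changes to planned methods, does not mention the matter, and SAP 1.8.5 lists supportive analyses as not applicable.

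**The concern.** The SAP describes a data-entry rule that can store a value its own scoring rules would reject, and then stops. A programmer working from it is not told whether to take the vendor's question 7 value or to rebuild it from the two parts. Nor does a reader of the report learn how many forms were involved.

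DLQI and DLQI 0/1 achievement are both secondary variables in SAP Table 1-10. SAP 1.8.3 plans no hypothesis tests, so the descriptive means and percentages are themselves the result. For a single absolute score, an error from failing to keep the most severe answer runs one way, towards better quality of life, and does not average out.

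**Working it through.** **Inputs, all from SAP 2.5.1.** Item scores run from 0 to 3, higher is worse, and the total is a plain sum. Question 7 'yes' scores 3, and a single unanswered question scores 0. The subscale maxima reproduce the stated maximum total: 6 + 6 + 6 + 3 + 6 + 3 = 30.

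**Reading assumed.** 7A is the yes / no / not relevant part and 7B the degree part (a lot = 2, a little = 1, not at all = 0). The SAP does not say which part the vendor's correction keeps, so all options are tried.

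**Step 1: error in question 7** = stored score minus the score under rules 3 and 4.

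| 7A | 7B | Rules 3 and 4 | 7A kept | 7B kept | Blanked, scored 0 |
|---|---|---|---|---|---|
| yes | a lot | 3 | 0 | -1 | -3 |
| yes | a little | 3 | 0 | -2 | -3 |
| yes | not at all | 3 | 0 | -3 | -3 |
| no / not relevant | a lot | 2 | -2 | 0 | -2 |
| no / not relevant | a little | 1 | -1 | 0 | -1 |
| no / not relevant | not at all | 0 | 0 | 0 | 0 |

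The last three rows each cover two 7A answers, so there are 9 pairs × 3 options = 27 cases. The error is 0 in 13, -1 in 5, -2 in 5 and -3 in 4. It is never positive. Relative to the 0 to 3 work/school subscale, the non-zero errors are 1/3 = 33% to 3/3 = 100% of the range.

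**Step 2: error in the total.** Let S be the sum of the other nine items (0 to 27), q the correct question 7 score and k ≤ q the stored score. There are 28 × (1 + 2 + 3 + 4) = 280 combinations. The stored total is lower in 28 × 6 = 168, equal in 28 × 4 = 112 and higher in none.

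**Step 3: DLQI 0/1.** A false achiever needs S + k ≤ 1 < S + q.
- S = 0: q = 2 or 3 with k = 0 or 1, so the correct total is 2 or 3.
- S = 1: q = 1, 2 or 3 with k = 0, so the correct total is 2, 3 or 4.

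False achievers therefore have correct totals of 2 to 4. Losing a true achiever would need k > q, which does not occur. As an example, a subject with nine zero items and 7A 'yes' has a correct total of 3, but counts as an achiever if 0 or 1 is stored.

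**Step 4: change from baseline** (absolute and percentage changes in the DLQI total are planned in SAP 2.1). Two hypothetical subjects:
- Correct 12 to 3 is (3 - 12)/12 = -75.0%. With baseline stored as 9 it becomes (3 - 9)/9 = -66.7%, which looks worse.
- Correct 12 to 4 is (4 - 12)/12 = -66.7%. With the later value stored as 1 it becomes (1 - 12)/12 = -91.7%, which looks better.

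The direction is not fixed for change scores.

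**Step 5: group level.** If a fraction f of forms at a visit is affected, the mean total is understated by at most 3f points and DLQI 0/1 overstated by at most f. For each 1% of forms affected, that is at most 0.01 × 3 = 0.03 points and 1 percentage point. The documents do not give f.

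**The case against.** The strongest reply is that the SAP already contains the right rule. If 7A and 7B are held separately and rules 3 and 4 are applied at derivation, the vendor's choice does no harm. No sentence says the vendor-resolved value is analysed. A reader might infer that it is, because no repair is described, but that inference rests on silence. This stands, and it is why the error above is conditional. It does not close the gap, because the SAP neither gives its own rules precedence nor says what was done.

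The effect may also be small. SAP 2.5.1 says the DLQI is very often completed accurately. Reaching the bound on DLQI 0/1 would require every affected form to cross the cut-off. With 7A 'yes', that means a subject prevented from working or studying whose other nine items sum to no more than 1. The mean bound requires a full 3-point error on every affected form. DLQI is a descriptive secondary outcome in a study whose primary objective is safety, and nothing suggests the vendor's rule worked differently by treatment. All of this limits the likely size. It does not replace a count.

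One narrow exception to the direction also stands. If the correction blanked question 7 and a second item was unanswered, the form would not be scored, and last observation carried forward could bring in a higher total. The SAP's wording, however, concerns selecting an answer, not deleting one.

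**Conclusion.** The point holds as a disclosed conflict between the vendor's entry rule and SAP scoring rules 3 and 4, with no stated handling. If vendor-resolved values are used and the correction stores one of the given answers, question 7 on an affected form is right or 1 to 3 points too low. Absolute totals and the work/school subscale can then only be understated and DLQI 0/1 achievement only overstated.

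A reader might go on to infer that all DLQI results are biased in the drug's favour, that the bias has a known size, or that it favours one arm. The documents support none of these. Change from baseline can move either way, the number of affected forms is not given, and no differential effect is shown. Specifying the handling is still worthwhile, because the remedy is cheap and removes a possible one-sided error from a secondary variable.

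**What to change.** In SAP 2.5.1, state that rules 3 and 4 override the vendor-resolved value. Wherever both 7A and 7B were answered, re-derive question 7 from the two responses in the vendor's digitised data as the higher-scoring one, before computing the subscale, total and DLQI 0/1. Apply this equally to the core baseline, so that change scores are consistent.

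Report the number of affected forms by visit and treatment group. Where the individual responses cannot be recovered but the affected forms can be identified, add a sensitivity analysis that sets question 7 to 3 on those forms. This is the most severe case and so bounds the effect.

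The cost is a query of the vendor's data and a small amount of extra programming, with no patient contact. Protocol 6.6.3 supports recovery: "The digitized paper will serve as source documentation", and the original questionnaires stay in the subject files. If the vendor did not keep the separate responses, going back to paper at 112 sites would be far more work. In that case the count and the sensitivity analysis are the proportionate choice.
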